#### 2. SYNOPSIS

Name of Sponsor/Company: Alkermes, Inc.

Name of Investigational Product: ALKS 4230

Name of Active Ingredients: ALKS 4230 and pembrolizumab

**Title of Study:** A Phase 2 Study of ALKS 4230 in Combination With Anti-PD-1 (Pembrolizumab) in Patients With Advanced or Recurrent Head and Neck Squamous Cell Cancer Currently on Treatment With Anti-PD-(L)1 Without Having Achieved a Complete Remission

With Anti-PD-(L)1 Without Having Achieved a Complete Remission		
Investigators:	(Coordinating Investigator),	other investigators at selected study sites
Study Period (Years): Approx	timately 2 years	Phase of Development: 2
Estimated date first patient enrolled: March 2019		
Estimated date last patient completed: February 2021		
Objectives:		
Primary:		

[figure not shown]
- To estimate the response rate to ALKS 4230 in combination with pembrolizumab in patients with squamous cell carcinoma of the head and neck (HNSCC) who have previously received anti-programmed cell death protein 1 (anti-PD-1) or anti-programmed cell death ligand-1 (anti-PD-L1) (henceforth referred to as PD-[L]1) therapy but who have not achieved a complete remission (CR). The primary objective will be assessed for the following 2 groups:
  - Group 1: Patients with stable disease (SD), defined as ≥12 weeks of SD per Response Evaluation Criteria in Solid Tumors (RECIST) v1.1 criteria, or patients with partial response (PR) with no further reduction in tumor size or response (ie, PR and not improving further) for ≥8 weeks on prior anti-PD-(L)1 therapy
  - Group 2: Patients with progressive disease (PD) with no prior response to anti-PD-(L)1 therapy after ≥8 weeks on anti-PD-1 therapy or patients currently with PD after prior achievement of a best response of SD or PR and after ≥8 weeks on anti-PD-(L)1 therapy

#### Secondary:

- To evaluate the duration of response (DOR), progression-free survival (PFS), time to progression (TTP), and overall survival (OS) of patients with advanced or recurrent HNSCC receiving pembrolizumab plus ALKS 4230
- To evaluate the safety and tolerability of pembrolizumab plus ALKS 4230

#### **Exploratory:**

- To evaluate whether assessment of pretreatment biopsies from patients who have failed to achieve a CR on therapy with anti-PD-(L)1 can identify a subset of patients who are likely to respond to the addition of ALKS 4230
- To evaluate whether a second biopsy, **beta**, can identify changes in tumors that will predict response or failure to the addition of ALKS 4230

The study plans to enroll patients in total . The number of patients enrolled into each cohort within each group will be determined at the time of enrollment, based on the patient's response to previous treatment. It will be at the discretion of Alkermes and the Immune Oncology Network (ION) to expand a particular cohort of interest. **Study Design Schematic 2** Pembrolizumab Pembrolizumab **ALKS 4230** Week 7 and Bevond: Daily I Daily IV Combo Q3W Week 1 Week 2 Week 3 Week 4 Week 5 Week 6 Pembrolizumab 200 mg q3weeks ALKS 4230 3 µg/kg daily IV Tumor Biopsy Week 2-3 if safe Abbreviations: IV=intravenous; Q3W=every 3 weeks. Dose delays and modifications for adverse events (AEs) related to the ALKS 4230 + pembrolizumab combination regimen are described in the protocol. After recovery from an AE that meets dose hold criteria, the patient may resume dosing at full dose of pembrolizumab and full or reduced dose of ALKS 4230 in subsequent cycles, with consultation from the ION and Alkermes Medical Monitors, or may discontinue from the study. Patients with tumors who respond to treatment will continue until the following: Confirmed progression occurs (upon agreement with the ION and Alkermes Medical Monitors, patients tolerating therapy and receiving clinical benefit may be allowed to stay on study for up to 1 year) Until unacceptable toxicity occurs Other criteria for discontinuation occur Safety and tolerability will be assessed and reported using standard Common Terminology Criteria for Adverse Events (CTCAE) v5.0 criteria. Safety will be monitored by the study Principal Investigator (PI), participating site PIs, the ION Coordinating Center PI and staff, and representatives from Alkermes. Number of Patients Planned: Main Criteria for Inclusion: Inclusion Criteria: Each patient must meet all of the following inclusion criteria to be qualified to participate in this study: 1. Is  $\geq 18$  years of age. 2. Is willing and able to provide informed consent. 3. Is willing and able to follow the study procedures as outlined in the protocol. 4. Must have a histologically or cytopathologically confirmed diagnosis of squamous cell carcinoma of the head and neck region that is locally advanced or recurrent and no longer

amenable to local surgical or radiation therapy and/or with evidence of metastatic disease. Both HPV-positive and -negative patients will be included.

- 5. Must have had prior PD-1:PD-L1 inhibition therapy with anti-PD-(L)1 therapy as the most recent systemic therapy with
  - a. (Group 1, Cohort 1) current SD (for  $\geq 12$  weeks by RECIST] criteria v1.1) or
  - b. (Group 1, Cohort 2) current PR with no further reduction in tumor size or response for ≥8 weeks (ie, PR and not further improving
  - c. (Group 2, Cohort 3) current PD with no prior response to anti-PD-(L)1 therapy after ≥8 weeks on anti-PD-(L)1 or
  - d. (Group 2, Cohort 4) current PD after prior achievement of a best response of SD or PR and after  $\geq 8$  weeks on anti-PD-(L)1 therapy.

Some minimal intervening localized palliative radiotherapy or ablation therapy may be allowed upon review and agreement by the ION and Alkermes Medical Monitors.

- 6. Must have disease that is measurable by RECIST v1.1 criteria as determined by the treating physician and not confounded by prior treatment such as radiation. Patients with only 1 site of disease must be able to provide adequate tissue samples at the time of biopsy that will not affect the tumor size per RECIST v1.1 criteria.
- 7. Patients who have received standard or investigational anti-PD-(L)1 agents as the most recent systemic therapy must wait at least 3 weeks (with the exception of an anti-PD-[L]1 inhibitor that is dosed every 2 weeks and in consultation with the ION and Alkermes Medical Monitors, in which case patients must wait at least 2 weeks) before enrollment into the study or 4 weeks if the half-life of the investigational agent is not known. Patients who have received standard or investigational agents other than anti-PD-(L)1 agents (including agents as part of a combination regimen with an anti-PD-[L]1 agent) must wait 8 weeks before enrollment into the study, unless discussed with and approved by the ION and Alkermes Medical Monitors on an individual basis.
- 8. Patients must be willing to provide tumor tissue adequate for biomarker correlative studies at the time points specified in the protocol.
- 9. Patients should have readily accessible tumor for biopsy pre- and post-pembrolizumab and ALKS 4230 combination regimen. Biopsy should be excisional, incisional, or core needle and large enough to show tissue architecture.
- 10. Have a performance status of ≤2 on the Eastern Cooperative Oncology Group Performance Scale.
- 11. Demonstrate adequate organ function. All screening laboratories should be performed within 10 days of treatment initiation.
- 12. Female patients of childbearing potential should have a negative urine or serum pregnancy test within 72 hours prior to receiving the first dose of study medication. If the urine test is positive or cannot be confirmed as negative, a serum pregnancy test will be required.
- 13. Is willing to abide by the contraception requirements for the duration of the study. Additional details pertaining to contraception requirements are detailed in the protocol.

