## 7. SELECTION AND WITHDRAWAL OF PATIENTS

Each patient must meet all of the inclusion and none of the exclusion criteria to be qualified to participate in this study.

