- 8. Patients must be willing to provide tumor tissue adequate for biomarker correlative studies at the time points specified in the protocol.

- 9. Patients should have readily accessible tumor for biopsy pre- and post-pembrolizumab and ALKS 4230 combination regimen. Biopsy should be excisional, incisional, or core needle and large enough to show tissue architecture.
- 10. Have a performance status of ≤2 on the Eastern Cooperative Oncology Group (ECOG) Performance Scale.
- 11. Demonstrate adequate organ function as defined in Table 3. All screening laboratories should be performed within 10 days of treatment initiation.

System	Laboratory Value
Hematological	
ANC	$\geq$ 1,000/µL without hematopoietic growth factor support
Platelet count	≥100,000/µL without transfusion support
Hemoglobin	$\geq 9 \text{ g/dL}$
Renal	
Serum creatinine OR	≤1.5×ULN OR
Measured or calculated a CrCl	
(glomerular filtration rate [GFR] can also	≥60 mL/min
be used in place of creatinine or CrCl)	
Hepatic	
	≤1.5×ULN OR
Serum total bilirubin	Direct bilirubin ≤ULN for patients with total bilirubin levels
	>1.5×ULN
AST and ALT	≤2.5×ULN OR
	$\leq$ 5×ULN for patients with liver metastases
Albumin	>2.5 mg/dL
Coagulation	
INR or PT aPTT	
 
≤1.5×ULN unless patient is receiving anticoagulant therapy.
 
If the patient is receiving anticoagulant therapy, the INR or PT needs to be within the therapeutic range of intended use of anticoagulants or deemed a safe level for the proposed biopsies by the biopsy surgeon or interventional radiologist.
 
≤1.5×ULN unless patient is receiving anticoagulant therapy. If the patient is receiving anticoagulant therapy, the aPTT needs to be within the therapeutic range of intended use of anticoagulants or deemed a safe level for the proposed biopsies by the biopsy surgeon or interventional radiologist.
 

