#### Table 3: Laboratory Values Defining Adequate Organ Function

Abbreviations: ALT=alanine aminotransferase; ANC=absolute neutrophil count; aPTT=activated partial thromboplastin time; AST=aspartate aminotransferase; CrCl=creatinine clearance; INR=international normalized ratio; PT=prothrombin time; ULN=upper limit of normal

a CrCl should be calculated per institutional standard.

- 12. Female patients of childbearing potential should have a negative urine or serum pregnancy test within 72 hours prior to receiving the first dose of study medication. If the urine test is positive or cannot be confirmed as negative, a serum pregnancy test will be required.
- 13. Is willing to abide by the contraception requirements for the duration of the study (additional details regarding contraception requirements are provided in Section 8.4.1).

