- 10. Has a history or current evidence of any condition, therapy, or laboratory abnormality that might confound the results of the study, interfere with the patient's participation for the full duration of the study, or is not in the best interest of the patient to participate, in the opinion of the treating Investigator.
- 11. Has known psychiatric or substance abuse disorders or a social situation that would interfere with cooperation with the requirements of the study.
- 12. Is pregnant or breastfeeding or expecting to conceive or father children within the projected duration of the study, starting with the Screening Visit through 120 days after the last dose of study drug (see Section 8.4.1 for additional details).
- 13. Known active infection with hepatitis B (hepatitis B surface antigen [HBsAg] reactive) or hepatitis C (hepatitis C virus [HCV] RNA [qualitative]) detected.
- 14. Has any finding that, in the view of the Investigator, would compromise the safety of the patient or affect their ability to adhere to the protocol visit schedule or fulfill visit requirements.
- 15. Is Investigator-site personnel, an immediate family of the Investigator-site personnel, employed by Alkermes or ION, or an immediate family member of an Alkermes or ION employee.
- 16. If, in the opinion of the Investigator (and/or Sponsor), the patient is unsuitable for enrollment in the study.
- 17. Has significant known cardiovascular impairment (New York Heart Association Congestive Heart Failure >Grade 2, unstable angina, myocardial infarction within the previous 6 months prior to the first dose of investigational drug, or existing serious cardiac arrhythmia).
- 18. Has chronic or acute gastrointestinal (GI) disorders resulting in diarrhea of any severity grade; patient is using chronic anti-diarrheal supportive care (more than 3 days/week) to control diarrhea in the 28 days prior to the first dose of investigational drug.
- 19. Has known cirrhosis diagnosed with Child-Pugh Class A or higher liver disease.

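### Protocol Section 7.1, Table 3: the albumin limit is printed as >2.5 mg/dL, so the albumin row excludes no patient as written (probably a unit misprint; minor)

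*Protocol*

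**What the plan says.** Inclusion criterion 11 appears twice in the protocol. The Synopsis gives the short form, "Demonstrate adequate organ function. All screening laboratories should be performed within 10 days of treatment initiation", with no table reference, albumin value or unit. Section 7.1 gives the operative form, "Demonstrate adequate organ function as defined in Table 3".

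Table 3, titled "Laboratory Values Defining Adequate Organ Function", is the only definition of adequate organ function in the two documents. Its hepatic block gives the albumin limit as >2.5 mg/dL. The cell is complete, with a number and a unit.

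Section 7 makes the criteria binding: "Each patient must meet all of the inclusion and none of the exclusion criteria to be qualified to participate in this study".

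Albumin is named in two other tables, Protocol Table 10 and SAP Table 1. Both list it as a chemistry analyte, without a limit or a unit. SAP Section 3.4 provides for a listing of protocol deviations, including those against the entry criteria.

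**The concern.** An eligibility limit is useful only if some candidate could fail it. At 2.5 mg/dL the albumin limit lies far below any level that a candidate for this trial could plausibly have, so the row appears in a binding table and screens nobody.

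Three things would be at stake:

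- An explicit numeric entry limit, presumably included for a reason, does nothing if the text is followed.
- The deviation listing in SAP Section 3.4 works from the entry criteria. With the printed limit it can never show an albumin deviation.
- A site that reads the number in another unit would be applying a rule that the protocol does not contain. It might turn away a patient whom the text admits, and the documents give no basis for settling the question.

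**Working it through.** **Inputs**

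- Printed limit: albumin >2.5 mg/dL (Protocol Section 7.1, Table 3).
- Conversion: 1 g/dL = 1,000 mg/dL; 1 g/dL = 10 g/L.
- Patient values: the documents give no albumin reference range. I assume 0.5 to 5.0 g/dL, set deliberately wide at the low end.

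The plan derives no figure here, so there is nothing to reproduce first. The check is a unit conversion and a comparison.

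**Step 1. Convert the limit.** 2.5 mg/dL ÷ 1,000 = 0.0025 g/dL, and 0.0025 × 10 = 0.025 g/L.

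**Step 2. Compare the assumed range with it.** Ratio = (albumin in g/dL × 1,000) ÷ 2.5.

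| Assumed albumin (g/dL) | In mg/dL | Ratio to printed limit | Meets the row as printed |
|---|---|---|---|
| 0.5 | 500 | 200 | yes |
| 1.0 | 1,000 | 400 | yes |
| 2.0 | 2,000 | 800 | yes |
| 2.5 | 2,500 | 1,000 | yes |
| 3.5 | 3,500 | 1,400 | yes |
| 5.0 | 5,000 | 2,000 | yes |

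Every value passes. To fail, a patient would need albumin at or below 0.0025 g/dL, which is 1/200 of the lowest value assumed.

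**Step 3. See whether the unit matters to the outcome.** For illustration only, if the same number were read in g/dL, assumed values from 0.5 to 2.5 would fail and values from 2.6 to 5.0 would pass. The two readings therefore give opposite answers over the lower part of the range. This does not show which limit or unit was intended.

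**Step 4. Look for a correction elsewhere.** The Synopsis criterion has no value. Protocol Table 10 and SAP Table 1 have neither limit nor unit. SAP Section 3.13.4 says that laboratory results will be reported in conventional US units, but that does not restate the limit. Nothing in either document overrides the Table 3 cell.

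**The case against.** The strongest reply is that this is a misprint any clinician would recognise. Sites would probably read the limit in g/dL or send a query, and little would happen in practice. That is likely, and it is the main reason for a minor grade. It does not make the cell correct, because the written rule is what entry-criteria deviations are judged against.

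The second reply is that other safeguards remain, and this stands. Exclusion 10 covers a patient who "Has a history or current evidence of any condition, therapy, or laboratory abnormality that might confound the results of the study" or for whom taking part is not in their best interest, as judged by the treating investigator. Exclusions 14 and 16 allow exclusion for a safety-relevant finding or for general unsuitability. Albumin is in the chemistry panel, and Protocol Section 8.3.11 requires laboratory results to be reviewed and judged acceptable before each dose. A markedly low value could therefore still keep a patient out. These routes rest on judgement, and none sets a common albumin limit.

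Some stronger readings are tempting, and the documents do not support them:

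- A reader might infer that the whole organ-function criterion is empty. It is not: the neutrophil, platelet, hemoglobin, renal, bilirubin, transaminase and coagulation limits in Table 3 are unaffected.
- A reader might infer that sites enrolled different populations, or that an electronic check was programmed with the wrong limit. Neither document shows how sites applied the row or contains an edit check, so both are conjecture.
- A reader might take hemoglobin being in g/dL in the same table as proof of the error. Different analytes may properly carry different units, so this only makes a misprint more likely. The argument rests on the size of the printed value.

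**Conclusion.** The point holds for one cell. As printed, the Table 3 albumin limit equals 0.0025 g/dL and excludes 0% of patients over an assumed range of 0.5 to 5.0 g/dL, with a margin of at least 200-fold. The range is my assumption, but the margin is so large that no reasonable alternative would change the conclusion. It follows that no albumin entry deviation could be flagged under SAP Section 3.4.

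A unit misprint is the likely explanation, though the documents alone cannot confirm it. The error is in an operative eligibility rule and not in background text, so it is worth correcting. It has no bearing on the primary analysis, the sample size or alpha. Severity is minor.

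**What to change.** The sponsor should confirm the intended albumin limit and its unit from its own source records and correct the albumin cell in Protocol Table 3. Any eligibility check built from that table, and the entry-criteria deviation check under SAP Section 3.4, should then be aligned with the corrected cell. The Synopsis wording needs no change, since it carries no value. No limit is proposed here.

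The cost is one table cell at the next protocol amendment and, if an electronic check exists, one update to it. If patients have already been enrolled, their screening albumin values should be compared with the confirmed limit, so that the deviation listing can state how it was applied.

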#### Exclusion Criteria:

Each patient must not have any of the following conditions to be qualified to participate in this study:

- 1. Has a diagnosis of immunodeficiency or is receiving systemic steroid therapy (inhaled or topical steroids are allowable) or any other form of immunosuppressive therapy within 7 days prior to the first dose of study drug.
- 2. Has active tuberculosis (TB; Bacillus tuberculosis).
- 3. Has hypersensitivity to pembrolizumab, ALKS 4230, or any of their excipients.
- 4. Has prior Grade ≥3 immune-related toxicities requiring systemic immunosuppressant treatment that were attributable or possibly attributable to PD-1 immune checkpoint blockade. Has toxicities deemed reversible from prior therapy, including anti-PD-1, that have not recovered to baseline or Grade ≤1. Patients with persistent Grade ≤2 neuropathy are an exception to this criterion and may qualify for the study.
  - a. **Note**: If patient received major surgery, the patient must have recovered adequately from the toxicity and/or complications from the intervention prior to starting therapy.
- 5. Has had a prior dose of anti-PD-(L)1 therapy within 3 weeks of Study Day 1, with the exception of an anti-PD-(L)1 inhibitor that is dosed every 2 weeks and in consultation with the ION and Alkermes Medical Monitors.
- 6. Has a known history of additional malignancy within 2 years or current additional malignancy that is progressing or requires active treatment. Exceptions include basal cell carcinoma of the skin or squamous cell carcinoma of the skin that has undergone potentially curative therapy, in situ cervical cancer, or treated prostate cancer with a prostate-specific antigen value of <0.01 ng/mL.
- 7. Has known active central nervous system metastases and/or carcinomatous meningitis. Patients with previously treated brain metastases may participate, provided that they are stable (without evidence of progression by imaging for at least 4 weeks prior to the first dose of study drug and any neurologic symptoms have returned to baseline), have no evidence of new or enlarging brain metastases, and are not using steroids for at least 7 days prior to study drug. This exception does not include carcinomatous meningitis, which is excluded regardless of clinical stability.
- 8. Has known history of, or any evidence of, non-infectious interstitial pneumonitis that required steroids or current pneumonitis, or oxygen requirement for any reason in the past 28 days.
- 9. Has an active major infection requiring systemic therapy within 1 week of starting study drug.
- 10. Has a history or current evidence of any condition, therapy, or laboratory abnormality that might confound the results of the study, interfere with the patient's participation for the full duration of the study, or is not in the best interest of the patient to participate, in the opinion of the treating Investigator.
- 11. Has known psychiatric or substance abuse disorders or a social situation that would interfere with cooperation with the requirements of the study.
- 12. Is pregnant or breastfeeding or expecting to conceive or father children within the projected duration of the study, starting with the Screening Visit through 120 days after the last dose of study drug.

- 13. Known active infection with hepatitis B (hepatitis B surface antigen [HBsAg] reactive) or hepatitis C (hepatitis C virus HCV RNA [qualitative]) detected.
- 14. Has any finding that, in the view of the Investigator, would compromise the safety of the patient or affect their ability to adhere to the protocol visit schedule or fulfill visit requirements.
- 15. Is Investigator-site personnel, an immediate family of the Investigator-site personnel, employed by Alkermes or ION, or an immediate family member of an Alkermes or ION employee.
- 16. If, in the opinion of the Investigator (and/or Sponsor), the patient is unsuitable for enrollment in the study.
- 17. Has significant known cardiovascular impairment (New York Heart Association Congestive Heart Failure >Grade 2, unstable angina, myocardial infarction within the previous 6 months prior to the first dose of investigational drug, or existing serious cardiac arrhythmia).
- 18. Has chronic or acute gastrointestinal disorders resulting in diarrhea of any severity grade; patient is using chronic anti-diarrheal supportive care (more than 3 days/week) to control diarrhea in the 28 days prior to the first dose of investigational drug.
- 19. Has known cirrhosis diagnosed with Child-Pugh Class A or higher liver disease.

Investigational Product, Dosage, Duration, and Mode of Administration:

Reconstituted ALKS 4230 is administered via a 30-minute IV infusion once daily for 5 consecutive days during the first week of each treatment cycle.

Pembrolizumab is to be administered as an IV infusion over 30 minutes in a dose of 200 mg Q3W, for up to 1 year for as long as patients are deriving clinical benefit (ie, objective response or SD) and tolerating therapy well.

Reference Therapy, Dosage, Duration, and Mode of Administration: None

**Duration of Study:** This study consists of a 28-day screening period, treatment period, and 30-day post-treatment follow-up. The treatment period consists of at least five 3-week cycles that can repeat for up to 1 year.

**Efficacy Endpoints:** The primary efficacy endpoint is the rate of new or improved antitumor response after the addition of ALKS 4230 treatment in patients receiving ongoing anti-PD-1 therapy but who have not achieved a CR.

The secondary efficacy endpoints in this study include:

- 1. Duration of response, progression-free survival, time to progression, rate of non-progression at 6 months, and OS
- 2. Antitumor response rate of subsets of patients based on disease status (PR, SD, or PD) at

screening

3. Antitumor activity as measured by radiological assessment compared to screening

